Background and rationale	
Persistent immune activation and inflammation in virologically suppressed HIV-infection are linked to excess cardiovascular risk and other non-communicable diseases. Cytomegalovirus (CMV) seropositivity is common in Indonesian people, including HIV-infected patients. However, treatment of CMV infection is not accessible for most patients.
 
Periodic asymptomatic CMV-reactive patients in HIV infected patients over a life time may contribute to non-AIDS defining morbidity, including cardiovascular disease, neurocognitive impairment, cancer and renal disease. Despite undetectable levels of HIV and CMV in plasma, these patients continue to have increased levels of biomarkers and immune activations.
 
Statin administration is supposed to reduce subclinical atherosclerosis by decreasing LDL cholesterol levels, possibly via lipid-independent anti-inflammatory effect. Its pleiotropic properties also adding beneficial effect against CMV infection. We plan to study atorvastatin in virally-suppressed HIV-infected patients on stable ART with CMV seropositive and statin-naïve to evaluate the subclinical atherosclerosis changes assessed by carotid intima media thickness (CIMT)

Primary Study objectives	To compare the effect of 48 weeks of 20 mg daily atorvastatin versus placebo on changes CIMT in virally suppressed HIV patients with CMV seropositivity
Secondary Study Objectives	
 1) To evaluate the interaction between baseline CMV copy number and effect of atorvastatin on CIMT changes 2) To evaluate the effect of 48 weeks of 20 mg daily

	
atorvastatin versus placebo on fasted lipid changes in virally suppressed HIV patients with CMV seropositivity
 
 3) To evaluate the effect of 48 weeks of 20 mg daily atorvastatin versus placebo on of brachial artery flow mediated vasodilatation (FMD) in virally suppressed HIV patients with CMV seropositivity 4) To evaluate the effect of 48 weeks of 20 mg daily atorvastatin versus placebo on liver fibrosis and steatosis changes in virally suppressed HIV patients with CMV seropositivity 5) To evaluate the effect of 48 weeks of 20 mg daily atorvastatin versus placebo on neurocognitive changes in virally suppressed HIV patients with CMV seropositivity 6) To evaluate the effect of 48 weeks of 20 mg daily atorvastatin versus placebo on several immune activation biomarkers (sCD14, VCAM, ICAM, hsCRP, and β2M) changes in virally suppressed HIV patients with CMV seropositivity 7) To evaluate the effect of 48 weeks of 20 mg daily atorvastatin versus placebo on oral periodontitis score changes in virally suppressed HIV patients with CMV seropositivity 8) To evaluate the interaction between baseline CMV copy number and effect of atorvastatin on FMD, neurocognitive function, liver fibrosis and steatosis, lipid profile, and immune activation biomarkers changes in 48 weeks

Participant population
	
HIV-positive patients on ART will be recruited from the HIV Integrated Care Unit, Cipto Mangunkusumo Hospital, Jakarta. Each participant must meet eligibility criteria as defined below in order to be enrolled in the study.
 
Inclusion criteria:
 
 1. Ages between 20 to 45 years old 2. Using stable ART at least 1 year 3. Positive IgG CMV 4. Viral load HIV RNA <50 copies / ml 
Exclusion criteria:
 
 1. Undergoing hepatitis C DAA therapy 2. Decompensated cirrhosis or acute liver failure 3. History of coronary artery disease 4. Diabetes mellitus 5. History of of brain infection, epilepsy, stroke 6. History of rhabdomyolysis or myopathy 7. Pregnant or breastfeeding 8. Severe depression 9. Using statin therapy in the past 6 weeks

	
10. History of statin hypersensitivity
 
11. Framingham Risk Score above 10% within LDL \geq130
 
12. Framingham Risk Score under 10% within LDL \geq160
 
13. Out of Periodontitis Index (Upper right molars, top series, upper left molars, lower right molars, bottom series, lower left molars)
 
Drop out criteria:
 
 1. Becomes pregnant during this study 2. Stop using ART > 1 month 3. Stop or refuse to continue to use atorvastatin during this study 4. Not willing to continue as participant in this study
Participating sites	HIV Integrated Care Unit, Tertiary Hospital Cipto Mangunkusumo
Study Design	This study using double blind randomized, placebo-controlled clinical trial. Subject chosen by consecutive methods.
Study Scheme or Intervention	Eligible subjects will be randomized to receive an atorvastatin or placebo with a ratio of 1: 1. Atorvastatin 20 mg or identical placebo capsules will be given orally for 48 weeks.
Schedule of Procedures/ Evaluations	
 1. The participants who meet the inclusion and exclusion criterias (except viral load, anti-CMV, and Framingham score criterias) get an explanation of the purpose, method of the study, the rights to stop or refuse to take part during in the study. And each participant gives their sign to ICF. 2. Viral load, IgG anti-CMV, fasted lipid profile, fasting glucose and insuline to define Framingham score will be done as screening process. 3. Participants with CMV seropositivity, undetectable viral load, and Framingham risk score $>$10% LDL $<$130 or Framingham risk score $<$10% LDL $<$160 will continue the study process. 4. Participants will be asked to fast for 10 hours before taking 12 mL of venous blood: for examination of blood glucose, ALT, CMV DNA, and sCD14, VCAM, ICAM, hsCRP, β2M, and transient elastography with CAP. CIMT, FMD, neurocognitive examination, and Community Periodontal Index will be done within a week before taking study drugs. 5. Participants will be randomized to get atorvastatin therapy or placebo. While using study drugs, participants continue their ART and other standard of cares. 6. Study drugs will be dispensed monthly along with ART refill and the pharmacist records the remaining

	
medication.
 
7. At week 24, blood collection procedures and neurocognitive examination procedures will be repeated.
 
8. At week 48, blood collection procedures, CIMT, FMD, transient elastography with CAP, neurocognitive examination, and community periodontal index procedures will be repeated.

Study Duration	
The study will be conducted from April, 2019 to April, 2021. Predicted accrual period: 4 months Enrollment of the first study participant to enrollment of last participant schedule on four months in the first year.

Primary Endpoint(s)	
The mean or median CIMT changes of virally suppressed HIV patients with CMV seropositivity in atorvastatin group versus placebo group between baseline and week 48

Secondary endpoints	
 - Magnitude of change in effect of atorvastatin on CIMT associated with baseline CMV copy number - The mean or median changes of fasted lipid between baseline and week 24, week 24 and week 48 - The mean or median changes of brachial artery flow mediated vasodilatation (FMD) between baseline and week 48 - The mean or median changes of liver fibrosis and steatosis in atorvastatin and placebo group between baseline and week 48 - The mean or median changes of sCD14, VCAM, ICAM, CRP, and β2M in atorvastatin and placebo group lipid between baseline and week 24, week 24 and week 48 - The mean or median changes of neurocognitive function in atorvastatin and placebo group lipid between baseline and week 24, week 24 and week 48 - The mean or median changes of oral periodontitis score in atorvastatin and placebo group between baseline and week 48 - Magnitude of change in effect of atorvastatin on FMD, neurocognitive function, liver fibrosis and steatosis, lipid profile, and immune activation biomarkers associated with baseline CMV copy number

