4.6.2. Exclusion Criteria

1. Undergoing for Hepatitis C DAA Therapy
2. Decompensated cirrhosis or acute liver failure
3. History of coronary artery disease
4. Diabetes mellitus
5. History of of brain infection, epilepsy, stroke
6. History of rhabdomyolysis or myopathy
7. Pregnant or breastfeeding
8. Severe depression
9. Using statin therapy in the past 6 weeks
10. History of statin hypersensitivity
11. *Framingham Risk Score* above 10% within LDL \geq 130
12. *Framingham Risk Score* under 10% within LDL \geq 160
13. Out of Periodontitis Index (Upper right molars, top series, upper left molars, lower right molars, bottom series, lower left molars)

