4.6.3 Drop Out Criteria

1. Pregnant during this study
2. Stop using ART > 1 month
3. Stop or refuse to use atorvastatin during this study
4. Not willing to continue as participant in this study

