4.13.1. Screening

Patients meeting the initial screening criteria will be test for HIV RNA (viral load), anti-CMV and fasting lipid profile:

- Age between 20 to 45 years old
- Using ART at least 1 year
- Not under hepatitis C therapy
- No history of coronary artery disease, brain infection, epilepsy, stroke
- No diabetes mellitus
- Not pregnant or breastfeeding
- Not severe depression (using mini ICD10)
- Not using statin therapy

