Fasting blood glucose and insulin		V	V	V	
DPL	V*				
LED	V*				
Store sample					
Serum		V	V	V	
Other Assessment					
Depression assessment	v				

*According to patient's symptom.

Blood volume collection

	Type	Blood collected	screening	randomization	Week 24	Week 48	Extravisit
1 Viral load	Plasma	3 mL	3 mL				
Lipid profile	Serum	2 mL	2 mL		2 mL	2 mL	
Fasting blood glucose	Serum	1 mL	1 mL		1 mL	1 mL	
IgG Anti-CMV	Serum	1 mL	1 mL				
Complete blood count	Plasma EDTA	3 mL		3 mL			
ALT, Creatine	Plasma EDTA	1 mL		1 mL			1 mL
CK	Plasma EDTA	1 mL		1 mL			1 mL
Storage sample	plasma	6 mL	5 mL	6 mL	9 mL	9 mL	
TOTAL volume			12 mL	12 mL	12 mL	12 mL	2 mL

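### The documents conflict on when fasting glucose is measured and never apply it to the diabetes exclusion, and no pregnancy test is scheduled although pregnancy is both an exclusion and a drop-out criterion

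*Combined protocol and SAP*

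**What the plan says.** **Criteria taken as met before testing.** Step 1 of the synopsis Schedule of Procedures/Evaluations reads: "The participants who meet the inclusion and exclusion criterias (except viral load, anti-CMV, and Framingham score criterias) get an explanation". Only viral load, CMV serology and the Framingham criterion are left for the tests. Section 4.13.1 agrees: absence of diabetes and of pregnancy or breastfeeding are on the list of conditions that come before the laboratory work.

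**Glucose.** Synopsis step 2 makes it a screening test, for a different purpose: "fasting glucose and insuline to define Framingham score will be done as screening process". Section 4.13.1 lists the screening tests without it: "Patients meeting the initial screening criteria will be test for HIV RNA (viral load), anti-CMV and fasting lipid profile". Synopsis step 4 takes it at baseline: "Participants will be asked to fast for 10 hours before taking 12 mL of venous blood: for examination of blood glucose, ALT, CMV DNA". Section 4.13.2 does the same. In the Appendix A schedule grid, the row "Fasting blood glucose and insulin" is marked at randomization, week 24 and week 48, and screening is blank. The blood-volume table in the same appendix allots 1 mL for glucose at screening, week 24 and week 48, and none at randomization.

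**Conditions for continuing after screening.** Synopsis step 3 begins "Participants with CMV seropositivity, undetectable viral load, and Framingham risk score" and adds the LDL limits. Section 4.13.2 uses the same conditions. Neither mentions glucose, diabetes or pregnancy.

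**Pregnancy.** Section 4.6.2 excludes patients who are "Pregnant or breastfeeding", and section 4.6.3 lists "Pregnant during this study" as a drop-out criterion. Eligible age is 20 to 45 years. No pregnancy test appears in the synopsis procedures, sections 4.13.1 to 4.13.5, or either table of Appendix A.

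**Eligibility review.** The grid marks a review of eligibility at screening, at randomization (visit 0) and at extra visits.

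**The concern.** An exclusion protects the trial only if something at entry can trigger it. For diabetes, a measurement exists, but its timing depends on which section the site follows, and no text says to use the result for this purpose. Section 1.1 names diabetes among the factors that affect change in CIMT, the primary endpoint. Diabetes is not a drop-out criterion, and section 6.2 analyses everyone as randomised. A patient with undiagnosed diabetes who is randomised would therefore stay in the comparison and could add the kind of variation the exclusion was meant to keep out.

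For pregnancy, no measurement exists at all. An early pregnancy that the participant does not know about would pass every step written in the protocol. What is at stake there is participant protection and the enforceability of the protocol's own exclusion, more than the primary analysis.

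**Working it through.** **1. Where each place puts the entry glucose sample**

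| Place | Screening | Baseline / visit 0 |
|---|---|---|
| Synopsis step 2 | yes, for Framingham score | – |
| Synopsis step 4 | – | yes, listed before randomization (step 5) |
| Section 4.13.1 | not listed | – |
| Section 4.13.2 | – | yes |
| Appendix A grid | blank | yes, in the randomization column |
| Appendix A blood-volume table | 1 mL | blank |

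The two tables of Appendix A contradict each other. The volume totals help to show what was intended:

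- Screening: 3 + 2 + 1 + 1 + 5 = 12 mL, the stated total. Without the 1 mL for glucose it is 11 mL.
- Randomization: 3 + 1 + 1 + 6 = 11 mL, against a stated 12 mL. A 1 mL glucose sample would close the gap, but none is listed.

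So the screening total requires glucose at screening. The randomization total leaves room for a second sample without listing it.

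**2. Is the result tied to the diabetes exclusion?** Step 2 uses glucose for the Framingham score. Step 3 and section 4.13.2 let patients continue on CMV IgG, viral load and Framingham/LDL. No glucose threshold or definition of diabetes is given. On every reading of the timing, the link to exclusion 4 is missing.

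**3. Is there a pregnancy result to review?** Scheduled visits are screening, visit 0, week 24 and week 48. A pregnancy test appears at 0 of 4. Severe depression is a useful contrast: section 4.13.1 names an instrument for it and Appendix A schedules the assessment at screening. Pregnancy has neither.

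**4. Size of the diabetes effect**

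The plan's own figure comes first. Section 4.5 gives a difference of 0.1, an SD of 0.12, a two-sample t-test, 5% significance and 90% power. Taken as two-sided, the t-test solution is 31.25, so 32 per arm, and 32 / 0.8 = 40 per arm. This reproduces the plan. Power at 32 per arm is 90.7%.

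The documents give no rate of undiagnosed diabetes. Assuming 1% to 5% among 80 randomised:

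- 0.01 × 80 = 0.8 patients
- 0.05 × 80 = 4 patients

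To illustrate the effect on power, assume further that such patients have twice the planned SD of CIMT change (0.24) and the same mean. With a fraction p of them, variance = (1 − p) × 0.12² + p × 0.24².

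| Patients of 80 | p | Variance | SD | Power at 32 per arm |
|---|---|---|---|---|
| 0 | 0 | 0.01440 | 0.1200 | 90.7% |
| 1 | 0.0125 | 0.01494 | 0.1222 | 89.6% |
| 4 | 0.05 | 0.01656 | 0.1287 | 86.4% |

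The loss is about 1 to 4 percentage points under a deliberately unfavourable assumption about the SD.

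No rate of unrecognised pregnancy is given either, and the number of women to be enrolled is not stated, so no count can be derived.

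**The case against.** A reader of the grid might infer that Appendix A fixes glucose at randomization, and that patients with diabetes will therefore be randomised and dosed untested. The documents do not support that:

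- The blood-volume table, in the same appendix, has glucose at screening, and so does synopsis step 2.
- Synopsis step 4 lists a further glucose sample before randomization at step 5, and a grid column does not fix the order of events within a visit.
- Section 5.2 has glucose run at once in the hospital laboratory, not stored.
- Section 4.11.2 can be read as leaving at least a week between randomization and first supply, so even a visit-0 result might be known before dosing.
- Eligibility is reviewed again at visit 0, and the synopsis requires every participant to meet the criteria. A clearly diabetic screening value could be acted on without further wording.
- Nothing says that diabetes is judged by history alone. Candidates have been on ART for at least a year and attend the clinic every month or two, so records exist.

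Most of this stands, and it removes the strong reading for diabetes. What survives is the contradiction itself, and the absence of any text that applies the result to exclusion 4. A site that follows section 4.13.1 and the grid has no study glucose result from screening, and a result that arrives after randomization would not remove the patient from the analysis.

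On pregnancy, participants are phoned every two weeks (section 4.10) and seen regularly in clinic (section 4.13.3). These contacts may bring a known pregnancy to light. They are not tests, and they come too late for entry. The review at visit 0 has no pregnancy result to look at.

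**Conclusion.** The point holds in two parts of different weight.

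**Glucose.** The timing is contradictory across the synopsis, sections 4.13.1 and 4.13.2, and the two tables of Appendix A, and no passage connects the result to the diabetes exclusion. On the grid reading, an undiagnosed patient could be randomised before a result is acted on. The number is unknown. At an assumed 1% to 5% it is 0.8 to 4 of 80, with power falling from 90.7% to between 89.6% (1 patient) and 86.4% (4 patients) if their SD is assumed to be double. This would add variation; no bias between arms is shown. It does not threaten the primary analysis.

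**Pregnancy.** Followed exactly, the protocol gives no objective check on exclusion 7 in women aged 20 to 45, before randomization or afterwards. An unrecognised early pregnancy could be randomised and exposed to study drug. How often this would happen cannot be estimated from the documents.

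Both should be corrected. The reason is enforceable eligibility and participant protection, with a minor gain in precision.

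**What to change.** 1. Reconcile synopsis steps 2 and 4, sections 4.13.1 and 4.13.2, and both Appendix A tables so that fasting glucose is a screening test. Its 1 mL is already in the screening total. If a baseline sample is also wanted, list it in the volume table. State what result counts as diabetes for this trial, and that it is checked against exclusion 4 before randomization.
2. Add a pregnancy result for women to the eligibility review before randomization, and show it in Appendix A. Use blood already drawn if volume allows. Screening is already at the 12 mL maximum of section 5.3, while the listed visit-0 samples sum to 11 mL, so the sponsor should confirm sample type and volume.
3. Reword synopsis step 1 and the conditions in step 3 and section 4.13.2 so that diabetes and pregnancy join viral load, CMV IgG and Framingham/LDL as criteria confirmed by test.
4. State how the pregnancy drop-out criterion is to be detected during follow-up. The method is for the sponsor to decide.

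The cost is a schedule and wording amendment with ethics approval, no additional blood for the screening glucose, a small assay cost per woman that the budget does not itemise, and a few more screen failures. The eligibility criteria and treatment rules do not change.

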1. INTRODUCTION

1.1. Background

HIV continues to be a major public health issue. In Indonesia, from January to March 2017 there were 10,376 people infected with HIV (PLWH). The highest percentage (87.2%) was in the productive-aged group (age 18 - 49 years).^{1,2} Antiretroviral therapy (ART) has contributed to significant reduction in morbidity and mortality of HIV patients, as evidenced by reducing AIDS-related deaths from 2.3 million in 2005 to 1.6 million in 2016.³ Free ART program conducted in Indonesia since 2004 had an impact on declining mortality of PLWH from 2.72% in 2013 to 1.22% at the end of 2014.⁴ Decreased morbidity and mortality due to AIDS is accompanied by an increase of non-communicable diseases (NCD) in PLWH.

Based on 10 years observational research, 10% of deaths in PLWH caused by cardiovascular disease, even 3 out of 4 PLWHAs had a low risk of the disease in the beginning of the observation.⁵ Increasing other NCD diseases, such as diabetes, neurocognitive disorder, chronic liver disease, chronic kidney disease, low bone mineral density, and other inflammatory related diseases, are associated with chronic immune and inflammatory activation that is still ongoing even in the state of viral suppression (undetectable viral load). Several antiretroviral drugs also increase to the worsening of these condition.

Cytomegalovirus (CMV) seropositivity is common in Indonesian people, including HIV-infected patients. In 2012, prevalence of CMV infection in pre-marital woman is 78,9%. In 2017, prevalence of CMV seropositivity is 98,23%.^{6,7} However, treatment of CMV infection is not accessible for most patients. Periodic asymptomatic CMV-reactive patients in HIV infected patients over a life time may contribute to non-AIDS defining morbidity, including cardiovascular disease, neurocognitive impairment, cancer and renal disease.⁸ Despite undetectable levels of HIV and CMV in plasma, these patients continue to have increased levels of biomarkers and immune activations.⁹

Atherosclerosis precedes cardiovascular events and has a prolonged asymptomatic phase during which the course of the disease can be modified by lifestyle modifications and treatment. The age of initiation and the rate of progression of atherosclerosis vary markedly among individuals and have been difficult to predict with traditional cardiovascular risk assessment models. Therefore, individuals with subclinical atherosclerosis should preferably be identified at an early stage, so that the primary prevention measures can be initiated. Early identification of subclinical atherosclerosis in individuals at low-to intermediate cardiovascular risk has been challenging.⁸ There are several markers of subclinical atherosclerosis including Carotid Intima-Media Thickness (CIMT), Coronary Artery Calcium Score (CACS), Ankle-Brachial Index (ABI), and Flow-Mediated Dilatation (FMD).¹⁰

As a surrogate marker for subclinical atherosclerosis, CIMT evaluation is a non-invasive examination using B-mode ultrasonography which relatively reproducible, easy and safely performed to detect early stages of atherosclerosis and is accepted as one of the best methods for evaluation of arterial wall structure. There are several factors affecting changes on CIMT including traditional risk factors such as age, sex, dyslipidemia, diabetes mellitus, etc and also novel risk factors including hereditary, certain genotypic indices, anthropometric parameters, rheumatoid arthritis, immunologic and inflammatory cytokines, yet socioeconomic position (SEP) and job stress.

Recent years, systemic inflammation and immune activation have gained attention as an emerged factors of atherosclerosis. HIV is one of the common risk factor of atherosclerosis. The direct correlation between CIMT and atherosclerosis among HIV-

positive patients had been established in several studies. A prospective study of 307 patients (179 HIV positive and 128 HIV negative) found that despite HIV suppression, lipid and hypertension control, HIV-positive patients have a disproportionately greater CIMT than HIV-negative comparators.¹¹ That facts parallel with one of our study which revealed that CIMT rose slightly in ART-naïve patients 12 months after commencing ART.¹² Cross-sectional study of 1183 HIV-infected patients compared with 297 HIV-uninfected patients from showed after multivariable adjustment for demographic characteristics and traditional cardiovascular risk factors, HIV infection was independently associated with subclinical atherosclerosis measured by CIMT.¹³ Cohort study from 1563 HIV-infected patients compared to 584 HIV-uninfected Patients patient showed CIMT among middle-aged (30-49 years and older adult (50 – 75 years) that were similar to or lower than those in HIV-uninfected participants. In contrast among those aged 6-29 years HIV infection was associated with higher CIMT.¹⁴

While HIV replication has been considered the major trigger of the immune system, persistent inflammation and immune activation have also found in patients receiving affective antiretroviral therapy (ART). Therefore, additional causes may elicit immune activation and might be involved in the accelerated course of atherosclerosis disease in virologically controlled HIV-infected patient. In HIV-infected patients, a relationship with subclinical atherosclerosis has been reported for CMV and herpes simplex virus type-2 (HSV-2). In HIV-infected patient, CMV antibody titers have been related to decreased artery distensibility and carotid lesion in women, but no association was found with the CIMT measurement.¹⁵

Statins are inhibitors of *hydroxyl-3-methylglutaryl coenzyme A* which were first extracted from *Pythium* sp, *Penicillium* sp, and *Aspergillus* sp. Initially, the target of statin therapy was to reduce cholesterol levels. Recent studies shown that the use of statin also associated with decrease other atherogenic lipid particles, such as oxidized LDL and phospholipase associated with lipoprotein.¹⁶ Statins remain key to primary and secondary CVD prevention; they improve endothelial function, slow the progression of atherosclerosis and stabilize atherosclerotic plaque. In the HIV population, decreased oxidized LDL is independently associated with a decrease in important markers of subclinical atherosclerosis, such as coronary plaque and carotid intima media thickness. The dual mechanism of statin use reduces LDL cholesterol, modifies inflammatory responses, antioxidant effects, antithrombic effects (clotting processes), and effects of removal of blood vessel plaques, thereby preventing cholesterol build-up and muscle proliferation.¹⁷ Treating dyslipidemia with statin has been challenging in people with HIV due to potential drug interaction between statin and antiretroviral drug due to competing cytochrome P450. A study comparing comparing pitavastatin and pravastatin in patients using protease inhibitor shown higher virological failure in pravastatin group. Therefore, guideline recommend pitavastatin as a preferred drug in the treatment of dyslipidemia in PLWH.¹⁸ However pitavastatin is expensive as it is not available in generic formulation. Atorvastatin, another moderate intensity statin is available in generic formulation and widely used in Indonesia. This drug has no interaction with all antiretroviral drugs use in Indonesia. Seropositivity to cytomegalovirus (CMV) may jointly predict increased mortality rate in patients with coronary heart disease (coronary heart disease). Statin therapy reduced lipid level and also has anti-inflammatory effect. Study showed statin reduce mortality rate among CMV-infected patients with CAD.¹⁹ In Vitro study demonstrated Statins has a broad anti-cytomegalovirus activity. All statins dose-dependently reduced CMV titers in human aortic endothelial cells. These findings provide new insight into beneficial effects of statins.²⁰

